4.4. End of Study Definition

A participant is considered to have completed the study if he/she has completed treatment phase (12 weeks) of the study.

The end of the study is defined as the date of the last assessment (16-week post-treatment follow-up) of the last participant in the study.

5. STUDY POPULATION

Prospective approval of protocol deviations to recruitment and enrolment criteria, also known as protocol waivers or exemptions, is not permitted.

5.1. Inclusion Criteria

Participants are eligible to be included in the study only if all of the following criteria apply:

Age

1. Between 5 and 17 years of age inclusive, at the time of informed consent

Type of Participant and Disease Characteristics

2. Chinese paediatric participants with SLE, who have completed 48 weeks treatment in study 213560 and who, in the opinion of the investigator, may benefit from treatment with GSK1550188.

Weight

3. Body weight ≥ 15 kg, at the time of signing the informed consent.

Sex and Contraceptive/Barrier Requirements

4. Male and/or female

No contraceptive measures are required for male participants.

Female participants:

A female participant is eligible to participate if she is not pregnant or breastfeeding, and at least one of the following conditions applies:

- Is not a woman of childbearing potential (WOCBP)
OR
- Is a WOCBP and is using a contraceptive method that is highly effective, with a failure rate of $<1\%$, as described in [Appendix 4](#) during the belimumab treatment period and for at least 16 weeks, corresponding to the time needed to eliminate any study intervention(s) (e.g., 5 terminal half-lives), after the last dose of study intervention. The investigator should evaluate the effectiveness of the contraceptive method in relationship to the first dose of study intervention.
- A WOCBP must have a negative highly sensitive [[Appendix 2](#)] pregnancy test (serum or as required by local regulations) within 35 days before the first dose of belimumab.

- The investigator is responsible for review of medical history, menstrual history, and recent sexual activity to decrease the risk for inclusion of a woman with an early undetected pregnancy.

Informed Consent

5. Participant signs and dates a written age appropriate assent form (in accordance with applicable regulations) and the parent or legal guardian (or emancipated minor) that has the ability to understand the requirements of the study, provides written informed consent (including consent for the use and disclosure of research-related health information) that the participant will comply with the study protocol procedures (including required study visits).

5.2. Exclusion Criteria

Participants are excluded from the study if any of the following criteria apply:

Medical Conditions

1. Have developed clinical evidence of significant, unstable or uncontrolled, acute or chronic diseases not due to SLE (i.e., cardiovascular, pulmonary, hematologic, gastrointestinal, hepatic, renal, neurological, malignancy or infectious diseases), or experienced an AE in 213560 study that could, in the opinion of the principal investigator, put the participant at undue risk.
2. Have developed any other medical diseases (e.g., cardiopulmonary), laboratory abnormalities, or conditions that, in the opinion of the principal investigator, makes the participant unsuitable for the study.
3. Have an estimated glomerular filtration rate as calculated by Schwartz Formula of less than 30 mL/min.
4. Have an IgA deficiency (IgA level <10 mg/dL).
5. Have a Grade 3 or greater laboratory abnormality based on the protocol toxicity scale (Section 10.2.1) except for the following that are allowed:
 - a) Stable Grade 3 hypoalbuminemia due to lupus nephritis and not related to liver disease or malnutrition.
 - b) Any grade proteinuria
 - c) Stable Grade 3 gamma glutamyl transferase (GGT) elevation due to lupus hepatitis and not related to alcoholic liver disease, uncontrolled diabetes or viral hepatitis. If present, any abnormalities in the alanine transaminase (ALT) and/or aspartate aminotransferase (AST) must be ≤Grade 2.
 - d) Stable Grade 3 neutropenia; or stable Grade 3 lymphopenia; or stable Grade 3 leukopenia, due to SLE

Diagnostic Assessments

6. Developing a positive test for HIV antibody after inclusion into 213560, per investigator's discretion according to clinical need.
7. Developing hepatitis B: Serologic evidence of Hepatitis B (HB) infection defined as Hepatitis B surface antigen positive (HBsAg+) OR Hepatitis B core antibody positive (HBcAb+) after inclusion into 213560, per investigator's discretion according to clinical need.
8. Developing a positive test for Hepatitis C antibody after inclusion into 213560, per investigator's discretion according to clinical need.

Prior/Concomitant Therapy

9. Have received a live or live-attenuated vaccine within 30 days of Day 1.

Other Exclusions

10. Are unable or unlikely, in the opinion of the investigator, to administer belimumab by SC injection and have no reliable source to administer the injection.

5.3. Lifestyle Considerations

No lifestyle restrictions are required during the course of this study.

5.4. Screen Failures

Screen failures are defined as participants who consent to participate in the clinical study but are not subsequently entered in the study. A minimal set of screen failure information is required to ensure transparent reporting of screen failure participants to meet the Consolidated Standards of Reporting Trials (CONSORT) publishing requirements and to respond to queries from regulatory authorities. Minimal information includes demography, screen failure details, eligibility criteria, any protocol deviations.

Individuals who do not meet the criteria for participation in this study (screen failure) may be rescreened once at the investigator's discretion following discussion with the medical monitor. Such participants will be assigned a new participant number and all screening assessments will be repeated.

**5.5. Criteria for Temporarily Delaying
Enrolment/Randomization/Administration of Study Intervention**

Not Applicable.

6. STUDY INTERVENTION(S) AND CONCOMITANT THERAPY

Study intervention is defined as any investigational intervention(s), marketed product(s), placebo, or medical device(s) intended to be administered to a study participant according to the study protocol.

6.1. Study Intervention(s) Administered

Table 1 Study Intervention(s) Administered

ARM Name	Open label arm
Intervention Name	Belimumab
Type	Biologic
Dose Formulation	SC Injection
Unit Dose Strength(s)	200 mg/mL
Dosage Level(s)	Dose weight ≥ 50 kg: 200 mg weekly; Dose weight ≥ 30 kg - < 50 kg: 200 mg every 10 days; Dose weight ≥ 15 kg - < 30 kg: 200 mg every 2 weeks
Route of Administration	SC injection (autoinjector)
Sourcing	Provided centrally by the Sponsor
Packaging and Labelling	Belimumab will be provided as an autoinjector
Manufacturer:	Autoinjector: The autoinjector components are manufactured by Scandinavian Health Limited (SHL) and assembled with the pre-filled syringe at GSK, Barnard Castle, UK.
Device	Single use autoinjector

6.1.1. Medical Devices

- The GSK manufactured medical devices (or devices manufactured for GSK by a third party) provided for use in this study are injection devices: an autoinjector device.

- GSK medical device incidents, including those resulting from malfunctions of the device, must be detected, documented, and reported by the investigator throughout the study.

6.2. Preparation, Handling, Storage and Accountability

1. The investigator or designee must confirm appropriate temperature conditions have been maintained during transit for all study intervention received and any discrepancies are reported and resolved before use of the study intervention.
2. Only participants enrolled in the study may receive study intervention and only authorized site staff may supply or administer study intervention. All study interventions must be stored in a secure, environmentally controlled, and monitored (manual or automated) area in accordance with the labeled storage conditions with access limited to the investigator and authorized site staff.
3. The investigator, institution, or the head of the medical institution (where applicable) is responsible for study intervention accountability, reconciliation, and record maintenance (i.e., receipt, reconciliation, and final disposition records).
4. Further guidance and information for the final disposition of unused autoinjectors are provided in the Study Reference Manual (SRM).
5. Under normal conditions of handling and administration, study intervention is not expected to pose significant safety risks to site staff. Take adequate precautions to avoid direct eye or skin contact and the generation of aerosols or mists. In the case of unintentional occupational exposure notify the monitor, Medical Monitor and/or GSK study contact.
6. A Material Safety Data Sheet (MSDS)/equivalent document describing occupational hazards and recommended handling precautions either will be provided to the investigator, where this is required by local laws, or is available upon request from GSK.
7. The excipients used in the pediatric formulation are safe for administration in the pediatric population participating in the study.

6.3. Measures to Minimize Bias: Randomization and Blinding

This is an open-label study without randomization and blinding.

6.4. Study Intervention Compliance

“Self-administration” is defined as administration of study drug either by the study participant or by the participant’s parent/caregiver. All participants less than 12 years old must have the study drug administered by their parent/caregiver. Whether the study drug is administered by the participant for those 12 years and older will be determined by the participant and his/her parents/caregivers.

Participants or their caregivers should not administer the study agent until they receive proper training in subcutaneous injection technique. Participants and caregivers who do not feel adequately trained with self-injection may return to the site for further training. Participants or caregivers who cannot administer the study drug may have subsequent

subcutaneous injections delivered by qualified study site personnel. Ideally, the injection site should be rotated between the left or right thigh and the abdomen.

6.4.1. Compliance with Subcutaneous Administration of Belimumab

Participants, caregivers or medical staff will be provided with an injection diary (refer to SRM). Dosing compliance must be reviewed with the participant/caregiver/medical staff at each site visit, the injection diary must be reviewed by study site staff and the entries transcribed to the electronic case report form (eCRF). Participants and caregivers are also required to return all used and any malfunctioning autoinjector devices. All unused autoinjectors, including spare devices, must be returned as described in the SRM.

When participants are dosed at the investigative site with belimumab, immediately after the injection, medical staff who inject the drug will complete the injection diary recording the date and time of injection, the injection site and whether or not the entire dose was administered. These injection diary entries will be transcribed into the eCRF by the site staff.

When participants self-administer study treatment(s) at home, immediately after the injection, participants or caregivers will complete the injection diary recording the date and time of injection, the injection site and whether or not the entire dose was administered. Participants must bring their injection diary with them to site visits and compliance with belimumab treatment will be assessed by the site staff through review of the injection diary and transcription of the entries into the eCRF.

A record of the number of belimumab autoinjectors dispensed to and taken by each participant and of unused autoinjectors returned by each participant must be maintained and reconciled with study treatment and compliance records. Used autoinjectors should be placed in a sharps container and returned to the site as described in the SRM. Any returned malfunctioning autoinjectors will be marked to distinguish them from the used autoinjectors (see SRM for details).

6.4.2. Missed Doses

If the participant has not taken the scheduled dose on the due date, the following rules apply:

Weekly dosing – if the scheduled dose has not been administered during the scheduled window the dose should be SKIPPED and dosing should be resumed on the next scheduled date.

10-day dosing – if the scheduled dose has not been administered during the scheduled window it may be administered up to 3 DAYS later. If the dose is not administered within 3 days, the dose should be SKIPPED and dosing should be resumed on the next scheduled date.

2 weekly dosing - if the scheduled dose is not administered during the scheduled window it may be administered up to 7 DAYS later. If the dose is not administered within 7 days the dose should be SKIPPED and dosing should be resumed on the next scheduled date.

The participant should not administer 2 doses on the same day and 2 doses should not be administered to make up for a dose missed.

If a participant misses 2 consecutive doses of belimumab or 3 non-consecutive doses of belimumab, then the Investigator must contact the Medical Monitor to discuss whether the participant should continue in the study (see SRM for details).

6.5. Dose Modification

No dose modifications of belimumab are allowed. Dosing frequency are fixed according the baseline body weight.

Dosing cohort	Dosing frequency
BW \geq 50 kg at baseline	Every week
BW \geq 30 kg and <50 kg at baseline	Every 10 days
BW \geq 15 kg and <30 kg at baseline	Every 2 weeks

BW= Body weight

6.6. Continued Access to Study Intervention after the End of the Study

Following the end of treatment at Week 12 or early withdrawal from the study, the participant will follow standard of care for SLE as determined by the investigator.

6.7. Treatment of Overdose

There is limited experience with overdosage of belimumab. Adverse reactions reported in association with cases of overdosage have been consistent with those expected for belimumab.

GSK does not recommend specific treatment for an overdose of belimumab.

In the event of a belimumab overdose, the investigator should:

- Contact the Medical Monitor immediately.
- Closely monitor the participant for AEs/SAEs.
- Document the quantity of the excess dose as well as the duration of the overdosing.

Decisions regarding dose interruptions or modifications will be made by the investigator in consultation with the Medical Monitor based on the clinical evaluation of the participant

6.8. Concomitant Therapy

Any medication or vaccine (including over-the-counter or prescription medicines, vitamins, and/or herbal supplements) that the participant is receiving at the time of screening or receives during the study must be recorded along with:

- reason for use
- dates of administration including start and end dates
- dosage information including dose, route and frequency

The Medical Monitor should be contacted if there are any questions regarding concomitant or prior therapy.

6.8.1. Permitted Medications and Non-Drug Therapies

The investigator may adjust concurrent medications (add, eliminate, change dose level/frequency) as clinically required during the study unless specifically excluded.

6.8.1.1. *Anti-malarials*

A new anti-malarial (e.g., hydroxychloroquine, chloroquine, quinacrine) may be started at any time during the study.

The dose of an anti-malarial may be reduced or increased as clinically required at any time during the study.

An anti-malarial may be replaced by another anti-malarial due to documented toxicity or lack of availability at any time during the study.

Anti-malarial drugs should be given according to local guidance (see SRM for further details).

NOTE: The use of anti-malarials for either SLE management or malarial prophylaxis is permitted.

6.8.1.2. *Steroids*

In this section, total systemic steroid dose is defined as the average daily dose of all steroids taken IV, IM, SC, intradermally and orally for both SLE and non-SLE reasons.

Systemic Steroids for SLE-related Disease Activity

The total dose of systemic steroids may be increased or decreased as clinically indicated at any time during the study. Treatment of SLE Flares with Steroids: If a participant has an SLE flare requiring an increase in steroid dose the investigator should consider the guidelines prepared for the American College of Rheumatology (ACR), for steroid dose/duration of induction therapy [[Liang, 2004](#)].

Intra-articular Injections of Corticosteroids

Participants may receive intraarticular (IA) corticosteroid injections at any time during the study.

Steroids for Reasons Other Than SLE Disease Activity

Inhaled and topical steroids are allowed throughout the course of the study.

Steroids may be given for reasons other than SLE disease activity (such as asthma, contact dermatitis) as clinically indicated.

6.8.1.3. Other Immunosuppressive/Immunomodulatory Agents

Starting any new allowable immunosuppressive/immunomodulatory agent is permitted at any time during the study.

The dose of existing immunosuppressive/immunomodulatory agents may be increased or decreased, as clinically required, at any time during the study.

An immunosuppressive/immunomodulatory agent may be replaced with 1 of the abovementioned agents due to documented toxicity or lack of availability. New topical immunosuppressive agents (e.g., eye drops, topical creams) are allowed at any time during the study.

6.8.1.4. Nonsteroidal Anti-inflammatory Drugs (NSAIDs)

During the study, NSAIDs may be given as clinically indicated (even if >1 week). An NSAID may be replaced with another NSAID due to documented toxicity or lack of availability.

Anti-thrombotic doses of aspirin are permitted at any time during the study.

Paracetamol (acetaminophen) is primarily an analgesic and lacks the anti-inflammatory properties of other NSAIDs. The use of paracetamol is recommended, when possible, to treat non-SLE-related conditions in the absence of a pre-existing hepatic function deficiency.

6.8.2. Prohibited Concomitant Therapy

Participants who start prohibited medications or therapies at any time during the study will be considered a protocol violation. Belimumab will be discontinued and participants will be withdrawn from the study.

The following medications and therapies are prohibited at any time during the study:

- Other investigational agents (biologic or non-biologic). Investigational applies to any drug not approved for sale in the country in which it is being used.
- Participation in a study using an investigational agent or non-drug therapy that may interfere with the conduct of this protocol (except study 213560)

- Anti- Tumor Necrosis Factor (TNF) or anti-IL-6 therapy (e.g., adalimumab, etanercept, infliximab, certolizumab, tocilizumab, golimumab).
- All biologics (e.g., rituximab, abatacept, interleukin-1 receptor antagonist).
- Janus kinase (JAK) inhibitors.
- Intravenous immunoglobulin (IVIG).
- IV cyclophosphamide (oral cyclophosphamide is permitted).
- Plasmapheresis, leukapheresis.
- Any live or live attenuated vaccines. (Participants who require a live or live attenuated vaccine during the study should have belimumab discontinued prior to receiving the vaccine).

7. DISCONTINUATION OF STUDY INTERVENTION AND PARTICIPANT DISCONTINUATION/WITHDRAWAL

7.1. Discontinuation of Study Intervention

If study intervention is permanently discontinued, the participant will complete the early withdrawal and follow-up visits as described in Section 8.1.4 and Section 1.3 (SoA) and will be withdrawn from the study.

Participants may be withdrawn from study agent and from the study if at any time:

- It is the wish of the participant (or their legally acceptable representative) for any reason.
- The investigator judges it necessary due to medical reasons.
- Consecutive belimumab injections (Section 6.4.2) or consecutive clinic visits are missed, consult to medical monitor to decide withdrawn or not (Section 8.1.4).

Furthermore, participants will be withdrawn from study agent and subsequently withdrawn from the study if at any time they:

- Become pregnant.
- Receive prohibited therapy
- Experience unacceptable toxicity
- Participate in another interventional clinical trial except Study 213560
- Trigger liver chemistry stopping criteria and/or IgG stopping criteria.

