2.3.1. Risk Assessment

Potential Risk of Clinical Significance	Summary of Data/Rationale for Risk	Mitigation Strategy
Investigational Product - GSK1550188/belimumab		
Infections		

As with other immunomodulators, the mechanism of action of belimumab, which results in a reduction in B-cells and IgG, may increase risk for the development of infections including severe infections, opportunistic infections and progressive multifocal encephalopathy (PML). Fatal infections have been reported in participants with SLE receiving immunosuppressant therapy, including belimumab.
	
The rate of serious infections for SLE is ~5% of participants receiving either belimumab or placebo.
	
Exclusions (see Section 5.2) based on history of primary immunodeficiency, IgA deficiency (IgA level <10 mg/dL), acute or chronic infections requiring management, serologic evidence of Hepatitis B, Hepatitis C or Human immunodeficiency virus (HIV) infection, and grade 3 (or greater) hypo gammaglobulinemia or (if unrelated to SLE) grade 3 (or greater) neutropenia, lymphopenia, leukopenia will be applied.
 
Participants whose IgG level falls below 250 mg/dL will have belimumab treatment withheld (See Section 10.2 Clinical Laboratory Assessments), and the appropriateness to continue dosing must be discussed and agreed with the Medical Monitor before the next dose. Any participant whose IgG level falls below 250 mg/dL and is associated with a severe or serious infection will have study agent permanently discontinued.
 
A diagnosis of PML should be considered in any participant presenting with new-onset or deteriorating neurological signs and symptoms.

Potential Risk of Clinical Significance	Summary of Data/Rationale for Risk	Mitigation Strategy
		
The participant should be referred to a neurologist or other appropriate specialist for evaluation. If PML is confirmed, discontinuation of belimumab should be considered. If PML is suspected, this should be reported to the Medical Monitor within 24 hours. The appropriateness of continuing belimumab dosing while the case is being assessed, should be discussed.

SC Injection-Related reactions, Hypersensitivity Reactions and Immunogenicity
		

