3. OBJECTIVES AND ENDPOINTS AND/OR ESTIMANDS

Objectives	Endpoints
Primary - Pharmacokinetics	

 To characterize belimumab exposure following belimumab 200 mg SC in Chinese paediatric systemic lupus erythematosus (SLE) participants who have previously been treated with IV belimumab 	
 Exposure parameters; $AUC_{ss, 0-T}$, $C_{avg,ss}$, $C_{min,ss}$, $C_{max,ss}$,
Secondary - Safety	

 To evaluate the safety and tolerability of belimumab 200mg SC in paediatric Participants with SLE who have previously been treated with IV belimumab 	
 Occurrence of adverse events, serious adverse events and adverse events of special interest through Week 12.

$AUC_{ss, 0-T}$ = Area under the curve at steady-state to the end of the dosing period, $C_{avg, ss}$ = Average serum concentration at steady state, $C_{min, ss}$ = Minimum serum concentrations at steady state, $C_{max, ss}$ = Maximum serum concentrations during the dosing interval at steady state

Primary estimands

For estimand strategy in primary endpoint. The estimand is described by the following attributes:

Population	Chinese paediatric participants 5-17 years of age with SLE who have previously been treated with IV belimumab
Treatment	
 Repeat doses of 200mg belimumab administered SC over 12 weeks on a background of standard of care therapy
Endpoints	
 Exposure parameters; $AUC_{ss, 0-T}$, $C_{avg,ss}$, $C_{min,ss}$, $C_{max,ss}$,
Summary Measure	
 Geometric mean
Intercurrent events and strategies	
The anticipated key intercurrent events and corresponding strategies are:
 
 Discontinuation of study medication: while-on-treatment strategy. The PK data after study medication discontinuation (except for PK data from EW visit) will not be used in analysis. Specially, to maximize PK data to support the estimation of

	
exposure parameters, the PK data from EW visit will be used in analysis.
 
 • Interruption of study medication: treatment policy strategy. The PK data after interruption of study medication will be used in analysis. • Using of prohibited medications or therapies: while-on-treatment strategy. Only the PK data before initiation of prohibited medications or therapies will be used in analysis.
--	---

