7.1.2. IgG Stopping Criteria

Any participant who has a Grade 4 IgG level (< 250 mg/dL), by the protocol-defined Adverse Event and Laboratory Value Severity Grade Scale (see Appendix 2, Section 10.2.1), will have dosing with study agent withheld, and the appropriateness to continue study treatment must be discussed with the Medical Monitor before the next dose. Any participant who has a Grade 4 IgG level associated with a severe or serious infection will have study agent discontinued and should complete the follow-up assessments as described in the SoA (Section 1.3).

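### Protocol 7.1 does not say which IgG finding forces withdrawal, so Grade 4 IgG without severe or serious infection can be read as withdraw or as withhold and discuss

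*Protocol*

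**What the plan says.** Three places in the protocol govern a low IgG result.

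- **Section 7.1, Discontinuation of Study Intervention.** The lead-in is mandatory: "participants will be withdrawn from study agent and subsequently withdrawn from the study if at any time they" meet any item on a list. One item is "Trigger liver chemistry stopping criteria and/or IgG stopping criteria". It states no grade, threshold or infection condition.
- **Section 7.1.2, IgG Stopping Criteria.** A participant with Grade 4 IgG (<250 mg/dL) "will have dosing with study agent withheld, and the appropriateness to continue study treatment must be discussed with the Medical Monitor before the next dose". A second sentence covers infection: "Any participant who has a Grade 4 IgG level associated with a severe or serious infection will have study agent discontinued".
- **Section 2.3.1, Risk Assessment.** The first tier is the same: "Participants whose IgG level falls below 250 mg/dL will have belimumab treatment withheld", with the condition that "the appropriateness to continue dosing must be discussed and agreed with the Medical Monitor before the next dose". The second tier, with severe or serious infection, is permanent discontinuation.

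Section 3 sets the PK handling. For "Interruption of study medication: treatment policy strategy" applies, and later PK data are used. After discontinuation, PK data are not used, except the sample from the early withdrawal (EW) visit.

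**The concern.** The only section that carries the name used in 7.1 is 7.1.2, and its opening sentence is about withholding, not stopping. A site that gets an IgG below 250 mg/dL in a child without a severe or serious infection can go to 7.1 and withdraw the child. It can also go to 7.1.2 or 2.3.1, withhold the dose and call the Medical Monitor. Both follow the text.

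At stake is consistent handling of one safety finding in a small paediatric study. A secondary matter is whether that child provides the late samples, which are those closest to the steady state that the primary endpoints describe. There is also a smaller mismatch: 2.3.1 requires the Medical Monitor's agreement before dosing goes on, and 7.1.2 requires only a discussion.

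**Working it through.** The point rests on no sample size or power figure, so the check sets the passages side by side and then traces the consequences through the schedule.

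**Step 1: the two clinical cases.**

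| Finding | 7.1 (read with the section it names) | 7.1.2 | 2.3.1 | Agree? |
|---|---|---|---|---|
| Grade 4 IgG with severe or serious infection | Withdraw | Discontinue | Discontinue permanently | Yes |
| Grade 4 IgG without such infection | Withdraw | Withhold, discuss | Withhold, discuss and agree | No |

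The conflict is confined to the second row.

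**Step 2: when it can matter.** The schedules of activities (section 1.3) place on-treatment IgG at Days 29, 57 and 85 for weekly and 2-weekly dosing, and at Days 31, 61 and 81 for 10-day dosing. The last dose is on Day 78 (weekly) or Day 71 (the other two groups). A result from the last visit therefore changes no dose. Only the first two checks count, apart from unscheduled tests.

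**Step 3: doses that depend on the reading.** This assumes that the dose due on the day of the IgG sample has already been given.

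- Weekly: after Day 29, seven doses remain (Days 36, 43, 50, 57, 64, 71, 78). After Day 57, three remain (64, 71, 78).
- Every 10 days: after Day 31, four remain (41, 51, 61, 71). After Day 61, one remains (71).
- Every 2 weeks: after Day 29, three remain (43, 57, 71). After Day 57, one remains (71).

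Withdrawal removes all of these. Withholding removes those that fall before any decision to resume.

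**Step 4: PK samples that depend on the reading.** Table 2 in section 8.5 puts samples 4 to 6 on Days 78, 81 and 85 (weekly), 71, 74 and 81 (10-day) or 71, 74 and 85 (2-weekly). All come after the first two IgG checks. A withdrawn child has an EW visit with the Week 12 assessments, which include PK, so these three samples are replaced by at most one. The 8-week and 16-week follow-up visits have no PK sampling. A child whose dosing is withheld and then resumed stays on schedule for all three.

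**Step 5: effect on the primary analysis set.** Samples 2 and 3 are due by Day 8, 11 or 15 (±2 days), before the first on-treatment IgG check. A child withdrawn at Day 29 or later would normally already meet the PK population definition in section 9.2, which needs one post-treatment sample. The child stays in the analysis, with less late information. One child is 1/17 = 5.9% of the planned sample.

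**Step 6: how likely.** Exclusion criterion 5 bars Grade 3 or greater laboratory abnormalities, and IgG is not among its exceptions. Grade 3 IgG is 250–399 mg/dL (section 10.2.1), so entrants have about 400 mg/dL or more. Falling below 250 needs a drop of more than (400 − 250)/400 = 37.5% within the treatment period. The documents give no expected frequency.

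**The case against.** The strongest reply is that the passages are compatible. Section 7.1 is a general list, 7.1.2 is its specific subsection, and only the second tier of 7.1.2 is stopping in the sense of 7.1. On any other reading the withhold-and-discuss sentences in 7.1.2 and 2.3.1 would have no purpose. The liver section also holds material under a stopping-criteria heading that allows continued therapy, so such a heading does not make everything beneath it a withdrawal trigger. Finally, both detailed passages route continuation through the Medical Monitor, which limits divergence between sites.

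Part of this stands. The compatible reading is plausible, and the Medical Monitor is a real safeguard. But no passage states that reading, and the layout gives a site reason to doubt it. Section 7.1 has a separate list of events after which participants may be withdrawn, and that list includes a case decided with the medical monitor. IgG was placed in the mandatory list instead. For liver chemistry, Appendix 6 separates stopping criteria from increased-monitoring criteria by name; for IgG, both actions share one heading. A site that withdraws a child directly under 7.1 could also bypass the Medical Monitor.

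A reader might go further and infer that the estimand mishandles these children, or that PK data already collected would be discarded. The documents do not support that. Section 3 already has separate strategies for interruption and discontinuation, and data follow the action actually taken. After a withdrawal the late samples would mostly never be collected, and the EW sample is kept.

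**Conclusion.** The inconsistency is real, narrow and minor. Section 7.1 does not identify which tier of 7.1.2 triggers withdrawal, so for Grade 4 IgG without severe or serious infection the protocol supports two different actions. The mismatch between discussion and agreement with the Medical Monitor belongs to the same point.

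It would be wrong to infer that the three sections conflict on every Grade 4 IgG result: with a severe or serious infection they agree on stopping.

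For an affected child the reading decides between one and seven remaining doses, depending on dosing group and on which check finds the result. It also decides between three late PK samples and at most one EW sample. This assumes a finding at one of the first two scheduled on-treatment checks. It also assumes, for the withholding route, that dosing resumes or sampling continues. The event is expected to be rare, and nothing in the documents supports a material effect on the primary exposure summary. The reason to act is consistent handling of a paediatric safety rule, and I take no view on which rule is right.

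**What to change.** Reconcile sections 7.1, 7.1.2 and 2.3.1 in the next amendment:

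1. Have the IgG item in 7.1 cite the exact condition that triggers withdrawal, so that 7.1 and 7.1.2 cannot be read differently for Grade 4 IgG without severe or serious infection.
2. Use the same wording in 7.1.2 and 2.3.1 for what is needed from the Medical Monitor before the next dose.

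The sponsor's clinical team decides which action applies to which finding. The intercurrent-event strategies in section 3 need no change. The cost is a few lines of text, with no effect on sample size, visits or analysis.
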